8.3.3 Safety Assessment and Use of the eVRC

All participants will be observed for 30 minutes after each vaccination for any immediate reactions. If any immediate AEs are observed during this period, the time at which the event occurred within this timeframe, as well as the event itself, any concomitant medications that were administered, and resolution of the event, must be recorded on the appropriate eCRF.

Participant's legally acceptable representative will use the eVRC (Section 8.1.9) to document the following information:

- Rectal temperatures measured Day 1 (day of vaccination) through Day 7 following each vaccination; Day 8 through Day 14 following each vaccination if fever is suspected
- Solicited injection-site AEs (swelling, redness, pain or tenderness, and hard lump) Day 1 through Day 14 postvaccination
- Solicited systemic AEs (irritability, drowsiness, appetite lost, and hives or welts) Day 1 through Day 14 postvaccination
- Any other unsolicited injection-site or systemic AEs Day 1 through Day 14 postvaccination
- The limb that was used for the administration of V114 or Prevnar 13™ (**Note:** the study will report injection-site AEs from V114 or Prevnar 13™ and not from concomitant injectable vaccines; the location of V114 or Prevnar 13™ administration can be used by the participant's legally acceptable representative to monitor the appropriate limb for injection-site AEs related to V114 or Prevnar 13™)
- Use of any analgesic or antipyretic on the day of vaccination
- Concomitant medications and nonstudy vaccinations Day 1 to Day 14 postvaccination

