Membership in Tier 2 requires that at least 1% of the participants in either treatment group exhibit the event. The threshold of at least 1% was chosen because when less than 1% of participants report AEs in both groups with more events in the V114 group, the 95% CI for the between-group difference in percent incidence will always include zero. Note that when less than 1% of participants report AEs in both groups but with more events in the Prevnar 13™ group or equal in both groups, the 95% CI for the between-group difference may exclude zero. However, the clinical significance of these differences is unknown given the small number of participants who report AEs in this situation (fewer than 4 subjects in each group) and; therefore, these AEs will be categorized as Tier 3 events. Because many 95% CIs for Tier 2 events may be provided without adjustment for multiplicity, the CIs should be regarded as a helpful descriptive measure to be used in review, not a formal method for assessing the statistical significance of the between-group differences in AEs and safety parameters that meet predefined limits of change.

In addition to individual events that occur in at least 1% of participants in any treatment group, the broad AE categories consisting of the proportion of participants with any AE, a vaccine-related AE, an SAE, a vaccine-related SAE, discontinuation due to an AE, and the proportion of participants who died will be considered Tier 2 endpoints.

Tier 3 Events

Safety endpoints that are not Tier 1 or 2 events are considered Tier 3 events. Only point estimates by treatment group are provided for Tier 3 safety parameters.

Table 4 Analysis Strategy for Safety Parameters

Safety Tier	Safety Endpoint [†]	p-Value	95% CI for Between-Group Comparison	Descriptive Statistics
Tier 1	Injection-site redness/erythema (Days 1 to 14)	X	X	X
	Injection-site swelling (Days 1 to 14)	X	X	X
	Injection-site tenderness/pain (Days 1 to 14)	X	X	X
	Injection-site hard lump/induration (Days 1 to 14)	X	X	X
	Irritability (Days 1 to 14)	X	X	X
	Drowsiness/somnolence (Days 1 to 14)	X	X	X
	Hives or welts/urticaria (Days 1 to 14)	X	X	X
	Appetite loss/decreased appetite (Days 1 to 14)	X	X	X
Tier 2	Any AE [†]		X	X
	Any Vaccine-Related AE [†]		X	X
	Any SAE [†]		X	X
	Any Vaccine-Related SAE [†]		X	X
	Discontinuation due to AE [†]		X	X
	Death [†]		X	X
	Maximum temperature measurements meeting the Brighton Collaboration cut points (Days 1 to 7)		X	X

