Tier 3	Specific AEs by SOC and PT [‡] (incidence ≥4 of participants in one of the vaccination groups)		X	X
	Specific AEs by SOC and PT [‡] (incidence <4 of participants in all of the vaccination groups)			X

[†] These endpoints are broad adverse event categories. For example, descriptive statistics for the safety endpoint of “Any AE” will provide the number and percentage of participants with at least one AE.
[‡] Includes only those endpoints not pre-specified as Tier 1 or not already pre-specified as Tier 2 endpoints.
 AE = adverse event; CI = confidence interval; PT = preferred term; SAE = serious adverse event; SOC = system organ class; X = results will be provided

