9.9.2 Sample Size and Power for Safety Analyses

The probability of observing at least one SAE in this study depends on the number of participants vaccinated and the underlying incidence of participants with an SAE in the study population. Calculations below assume that 100% of the randomized participants will be evaluable for safety analyses. There is an 80% chance of observing at least one SAE among 2,000 participants in V114 group if the underlying incidence of an SAE is 0.08% (1 of every 1243 participants receiving the vaccine). There is a 50% chance of observing at least one SAE among 2,000 participants in V114 group if the underlying incidence of an SAE is 0.03% (1 of every 2,886 participants receiving the vaccine). If no SAEs are observed among 2,000 participants, this study will provide 97.5% confidence that the underlying percentage of participants with an SAE is <0.18% (one in every 543 participants).

[Table 6](#) summarizes the percentage point differences between the 2 vaccination groups that could be detected with 80% probability for a variety of hypothetical underlying incidences of an AE. These calculations assume 2,000 participants in V114 group and 400 participants in Prevnar 13™ group, and are based on a 2-sided 5% alpha level. The calculations are based on an asymptotic method proposed by Farrington and Manning (1990) [Farrington, C. P. 1990]; no multiplicity adjustments were made.

Table 6 Differences in Incidence of Adverse Event Rates Between the 2 Vaccination Groups That Can be Detected With an ~80% Probability (Assuming 2-sided 5% Alpha Level with 2000 Participants in V114 Group and 400 Participants in Prevnar 13™ Group)

Incidence of Adverse Event		Risk Difference
V114 (%)	Prevnar 13™ (%)	Percentage Points
1.6	0.1	1.5
4.9	2	2.9
9.0	5	4.0
15.2	10	5.2
21.0	15	6.0
26.6	20	6.6
37.3	30	7.3

Incidences presented here are hypothetical and do not represent actual adverse experiences in either group. Based on an asymptotic method proposed by Farrington and Manning (1990) [Farrington, C. P. 1990]

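### Unsolicited adverse events are collected separately but never compared between groups as a class; the only all-AE rows also count solicited events, which dilutes any difference

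*Combined protocol and SAP*

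**What the plan says.** Protocol 8.3.3 lists the eight solicited events (four injection-site, four systemic) and then, as a separate eVRC item, "Any other unsolicited injection-site or systemic AEs Day 1 through Day 14 postvaccination".

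Protocol 9.6.2 and sSAP 3.6.2 put each of the eight solicited events in Tier 1, with a p-value and a 95% CI. The broad Tier 2 categories are "the broad AE categories consisting of the proportion of participants with any AE, a vaccine-related AE, an SAE, a vaccine-related SAE", together with discontinuation due to an AE and death. The footnote to both analysis tables says that the 'Any AE' row "will provide the number and percentage of participants with at least one AE"; nothing removes solicited events from that count. Maximum temperature has its own Tier 2 row.

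Other AEs are handled by system organ class (SOC) and preferred term (PT). A between-group CI is given when incidence reaches 1% in either group, and only point estimates below that. (Protocol Table 4 prints the cut-off as 4 rather than 1%; the protocol text and sSAP Table 3 use 1%.)

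The safety endpoint lists in protocol 9.4.2 and sSAP 3.4.2 contain no unsolicited category. The sSAP adds a supportive comparison of solicited complaints (3.6.2) and subgroup summaries of overall and solicited AEs (3.10), but nothing for unsolicited AEs overall.

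**The concern.** An infant with one solicited symptom in any of four 14-day windows is already an event in 'Any AE'. A later unsolicited event in that infant adds nothing to the row. Only infants with no solicited event can carry an unsolicited difference into it, so the difference shrinks as solicited events become more common. The same mechanism acts in 'Any Vaccine-Related AE', where solicited events count if they are judged related.

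The protocol's stated purpose is to compare the safety of V114 with that of Prevnar 13 and to contribute to a robust safety database (2.1). An excess of unsolicited AEs spread thinly over many terms could leave the all-AE rows looking balanced. The missing proportion cannot be rebuilt from the term-level tables, because one infant may appear under several terms. If it were first produced after unblinding, it would be a post hoc analysis under protocol section 9.

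**Working it through.** **Inputs from the documents (protocol 9.9.2).** "These calculations assume 2,000 participants in V114 group and 400 participants in Prevnar 13™ group, and are based on a 2-sided 5% alpha level". Evaluability: "Calculations below assume that 100% of the randomized participants will be evaluable for safety analyses". The method is Farrington-Manning, which at a null difference of zero is the pooled-variance formula.

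**Assumed, because the documents do not give them.** S, the proportion with at least one solicited AE, taken as equal in both groups and independent of unsolicited AEs; and the unsolicited incidences, borrowed from the hypothetical pairs in Table 6.

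**Step 1: reproduce Table 6.** With V for V114 and P for Prevnar 13:

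- pooled p = (2000·pV + 400·pP)/2400
- SE0 = √[p(1−p)(1/2000 + 1/400)]
- SE1 = √[pV(1−pV)/2000 + pP(1−pP)/400]
- power = Φ[(pV − pP − 1.96·SE0)/SE1]

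For 37.3% v 30%: p = 0.3608, SE0 = 0.02630, SE1 = 0.02534, so power = Φ[(0.073 − 0.05155)/0.02534] = Φ(0.846) = 80.1%. The seven rows of Table 6 give 79.1% to 80.5%, so the table reproduces.

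**Step 2: the same difference inside 'Any AE'.** Any AE = S + (1−S)·u, where u is the unsolicited proportion. The difference is therefore multiplied by (1−S). At S=50% the row compares 68.65% with 65.0%: p = 0.6804, SE0 = 0.02554, SE1 = 0.02601, so power = Φ[(0.0365 − 0.05006)/0.02601] = Φ(−0.521) = 30.1%.

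| S | Any AE, V114 v Prevnar 13 (%) | Difference (points) | Expected M&N 95% CI | Power |
|---|---|---|---|---|
| 0 (unsolicited alone) | 37.3 v 30.0 | 7.30 | 2.19 to 12.10 | 80% |
| 20% | 49.8 v 44.0 | 5.84 | 0.47 to 11.11 | 57% |
| 50% | 68.7 v 65.0 | 3.65 | −1.32 to 8.85 | 30% |
| 70% | 81.2 v 79.0 | 2.19 | −1.93 to 6.76 | 18% |
| 80% | 87.5 v 86.0 | 1.46 | −1.97 to 5.45 | 13% |
| 90% | 93.7 v 93.0 | 0.73 | −1.69 to 3.81 | 9% |

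For 15.2% v 10%, power falls from 80% alone to 37% at S=20%, 16% at S=50%, 8% at S=80% and 6% at S=90%.

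**Step 3: can the term-level rows stand in?** Spread 37.3% v 30% evenly over k independent terms, so that each term has incidence 1 − (1−u)^(1/k):

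- k=10: 4.56% v 3.50%, power 13% per term
- k=20: 2.31% v 1.77%, power 8% per term
- k=50: 0.93% v 0.71%, expected below 1% in both groups, hence no CI

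**Step 4: organ-class rows.** These add up the terms within a class.

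- One class carries the whole excess, with 10% in the comparator: the V114 incidence is 1 − 0.627/(0.70/0.90) = 19.4%, and power exceeds 99%.
- Three independent classes: 14.4% v 11.2% each, power 39% each; the chance that at least one CI excludes zero is 77%.
- Five classes: 8.9% v 6.9% each, power 25% each; the chance is 76%.
- With no true difference, the chance that at least one CI excludes zero is already 1 − 0.95³ = 14% for three classes and 1 − 0.95⁵ = 23% for five.

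**The case against.** The strongest reply is that unsolicited AEs are compared, only not in one row. Section 9.6.2 tiers organ-class terms as well as specific terms, so an excess within one body system is summed and given a CI, and Step 4 shows this can be a sensitive route. SAEs, vaccine-related SAEs, discontinuations, deaths and temperature have rows of their own. All of this stands, and it rules out the inference that unsolicited harm goes uncompared. It does not supply an overall estimate: a 77% chance that some organ-class interval excludes zero must be read against 14% by chance alone, and it gives no figure for the class as a whole.

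A reader might also infer that 'Any AE' cannot show an unsolicited difference because solicited symptoms swamp it. The documents state no solicited incidence, so they do not support that. At S=10% power is still 68%, and at S=30% it is 47%.

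Nor do the documents support reading this as a failure to analyse the primary endpoints. Those are solicited injection-site AEs, solicited systemic AEs and vaccine-related SAEs, and all receive between-group CIs. Overall unsolicited incidence is not a listed endpoint.

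Two further objections have force. Power is an imperfect yardstick where the plan has no formal hypothesis and calls its intervals descriptive; here it only measures how much sensitivity the composite loses. And an unsolicited row would itself be mixed: fever is not among the eight solicited events, and reactions to non-study vaccines and ordinary infant illness would enter it. The fever rule therefore has to be written down.

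**Conclusion.** The gap is real and is the same in the protocol and the sSAP: unsolicited AEs as a class have no between-group comparison, and both all-AE rows mix them with solicited events. A concentrated excess could be seen elsewhere in the plan; a diffuse one has no single undiluted estimate.

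Under equal and independent solicited incidence the direction of the dilution is certain, but its size rests on an S that the documents do not give. Within that model, an unsolicited difference detectable with 80% power alone drops to 57% (for 37.3% v 30%) or 37% (for 15.2% v 10%) at S=20%, and to 30% or 16% at S=50%. A positive association between solicited and unsolicited events would dilute more, and a negative one less. Nothing was computed for 'Any Vaccine-Related AE', where the loss depends on how many solicited events are judged related.

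This is a gap in safety description that can be closed cheaply. It is not an error in a confirmatory test, since the plan has none.

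**What to change.** In protocol Table 4 and sSAP Table 3, add two Tier 2 rows: 'Any unsolicited AE (Days 1 to 14)' and 'Any vaccine-related unsolicited AE (Days 1 to 14)'. Give each the Miettinen-Nurminen difference and 95% CI in the APaT population.

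Define unsolicited as any AE other than the eight Tier 1 solicited events. State whether fever reported as an AE is counted, since temperature already has its own row. Keep the existing rows unchanged.

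The data are already collected, so no visit, form or sample-size change is needed. The cost is two more unadjusted descriptive intervals, which the plan already accepts for Tier 2.

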9.6.3 Demographic and Baseline Characteristics

The comparability of the vaccination groups for each relevant demographic and baseline characteristic will be assessed by the use of summary tables. No statistical hypothesis tests will be performed on these characteristics. The number and percentage of participants screened and randomized and the primary reasons for screening failure and discontinuation will be displayed. Demographic variables (e.g., age, race, and gender, birth weight [kg], gestational age), baseline characteristics, prior and concomitant vaccinations and therapies will be summarized by vaccination group either by descriptive statistics or categorical tables. Demographic variables and baseline characteristics will also be summarized for the Premature Infant Immunogenicity Substudy.

9.7 Interim Analyses

A periodic review of safety and tolerability data across the V114 Phase 3 pediatric program will be conducted by an independent, unblinded, external DMC. A description of the structure, function, and guidelines for decision-making by the DMC, along with the timing and content of the safety reviews will be outlined in the DMC charter. Information regarding the composition of the DMC is provided in Appendix 1. There are no plans to conduct an interim analysis of unblinded immunogenicity data in this study. However, unblinded immunogenicity data from this study and other ongoing V114 clinical studies will be made available to the DMC upon request to enable a benefit-risk assessment.

Study enrollment is likely to be ongoing at the time of any interim analyses. Blinding to intervention assignment will be maintained at all investigational sites. The results of interim analyses will not be shared with the investigators prior to the completion of the study. Participant-level unblinding will be restricted to an external unblinded statistician performing interim analyses.

The DMC will serve as the primary reviewer of the results of the safety interim analyses and will make recommendations for discontinuation of the study or protocol modifications to an executive committee of the Sponsor (see Appendix 1 for details on the Committees Structure for this study). If the DMC recommends modifications to the design of the protocol or discontinuation of the study, this Executive Oversight Committee (EOC) of the Sponsor (and potentially other limited Sponsor personnel) may be unblinded to results at the intervention level in order to act on these recommendations. The extent to which individuals are unblinded with respect to results of interim analyses will be documented by the external unblinded statistician. Additional logistical details will be provided in the DMC Charter.

Intervention-level results from the safety interim analysis will be provided by the external unblinded statistician to the DMC. Prior to final study unblinding, the external unblinded statistician will not be involved in any discussions regarding modifications to the protocol, statistical methods, identification of protocol deviations, or data validation efforts after the interim analyses.

9.8 Multiplicity

No multiplicity adjustment is planned as there is no formal hypothesis testing.

9.9 Sample Size and Power Calculations

9.9.1 Sample Size and Power for Immunogenicity Analyses

Immunogenicity analyses are for Premature Infant Immunogenicity Substudy only and considered as secondary objectives in this study. All immunogenicity objectives are descriptive endpoints. The study will randomize premature infants in a 1:1 ratio to either V114 or Prevnar 13™ vaccination group. The sample size of Premature Infant Immunogenicity Substudy will be approximately 1% to 2% of the total enrolled participants. The width of the within-group 95% CIs for the serotype-specific IgG GMCs depends on the

sample size, variability of the natural log concentrations, and the magnitude of the IgG GMC. For demonstration, it is assumed that 25 participants in each vaccination group will be enrolled and 22 participants will be evaluable for PP immunogenicity analyses at 30 days PD3, prior to Dose 4, and 30 days PD4 (based on the 90% evaluability rate). The 95% CIs based on the assumed number of evaluable subjects for various hypothetical IgG GMCs at 30 days PD3, prior to Dose 4, and 30 days PD4 and various hypothetical standard deviation estimates for the natural log titers are displayed in [Table 5](#).

Table 5 Within-Group 95% CIs for Varying Hypothetical IgG GMCs and Varying Standard Deviations

Standard Deviation of Natural Log Titers [†]	Serotype-specific IgG GMCs [†]		
	1	5	10
	V114 or Prevnar 13™	V114 or Prevnar 13™	V114 or Prevnar 13™
1.0	(0.64, 1.56)	(3.21, 7.79)	(6.42, 15.58)
1.5	(0.51, 1.94)	(2.57, 9.72)	(5.14, 19.45)
2.0	(0.41, 2.43)	(2.06, 12.14)	(4.12, 24.27)

Based on 22 evaluable participants in either V114 group or Prevnar 13™ group.
[†] The estimates of the standard deviation and IgG GMCs are representative of those observed in previous MSD study.
 CI = confidence interval; GMC = Geometric Mean Concentration; IgG=Immunoglobulin G.

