4 STUDY DESIGN

4.1 Overall Design

Approximately 2,400 healthy infants will be randomly assigned to receive V114 (n \approx 2,000) or Prevnar 13™ (n \approx 400) at Visits 1, 2, 3, and 5 (approximately 2, 4, 6, and 12 to 15 months of age, respectively) in the following ratios based on gestational age:

- Full-term infants (gestational age ≥ 37 weeks) 5:1 to V114 or Prevnar 13™
- Premature infants (gestational age < 37 weeks) 1:1 to V114 or Prevnar 13™

It is estimated that approximately 1 to 2% of the overall study population will have a gestational age <37 weeks and will be eligible for inclusion in the Premature Infant Immunogenicity Substudy. There is no prespecified number of premature infants targeted for enrollment in the substudy.

Participants will be followed for local and systemic AEs through Day 14 following each vaccination with V114 or Prevnar 13™. Information for SAEs and deaths, regardless of whether the events are considered to be vaccine-related by the investigator, will be collected from the time consent is signed through completion of participation in the study. An external Data Monitoring Committee (DMC) will conduct a periodic review of safety and tolerability data for the V114 Phase 3 pediatric program. A description of the structure, function, and guidelines for decision making by the DMC, along with the timing and content of the safety reviews will be outlined in the DMC charter. Information regarding the composition of the DMC is provided in Appendix 1.

In addition to the safety assessments, participants in the Premature Infant Immunogenicity Substudy, will also have blood samples for immunogenicity assays drawn at 3 timepoints: (1) 30 days Postdose 3 (PD3), (2) immediately prior to Dose 4, and (3) 30 days Postdose 4 (PD4).

After completion of immunogenicity testing, serum samples will be stored to conduct any additional study-related testing as required by regulatory agencies or the Sponsor. For randomized study participants who provided consent for future biomedical research, leftover sera from the study may be used for the development and/or validation of pneumococcal assays after completion of all study-related immunogenicity testing.

Specific procedures to be performed during the study, as well as their prescribed times and associated visit windows, are outlined in the SoA in Section 1.3. Details of each procedure are provided in Section 8.

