Statistical Methods for Key Safety Analyses	
P-values (Tier 1 endpoints) and 95% CIs (Tier 1 and Tier 2 endpoints) will be provided for between-vaccination group differences in the percentage of participants with events; these analyses will be performed using the M&N method [Miettinen, O. and Nurminen, M. 1985].

Interim Analyses	
To support the periodic review of safety and tolerability data across the V114 Phase 3 program, an external unblinded statistician will provide unblinded interim safety summaries to an independent DMC for their review. There are no plans to conduct an interim analysis of unblinded immunogenicity data in this study. However, unblinded immunogenicity data will be made available to the DMC upon request to enable a benefit-risk assessment.

Multiplicity	
No multiplicity adjustment is planned.

Sample Size and Power	
Immunogenicity: The immunogenicity objectives for this study are descriptive secondary objectives for the Premature Infant Immunogenicity Substudy only. The study will randomize premature infant participants in a 1:1 ratio to either V114 or Prevnar 13™ vaccination group. The sample size of the Premature Infant Immunogenicity Substudy will be approximately 1% to 2% of overall participants. There is no hypothesis to be evaluated for immunogenicity objectives. Section 9.9.1 provides information about the expected variability of the IgG GMC given the sample size.
 
Safety: Section 9.9.2 provides information about the ability of this study to estimate the incidence of AEs within and between the vaccination groups.

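### Does the premature-infant precision table assume more infants per group than the design expects?

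*Combined protocol and SAP*

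**What the plan says.** Protocol Section 4.1 gives the total ("Approximately 2,400 healthy infants will be randomly assigned to receive V114", or the comparator) and the premature share: "It is estimated that approximately 1 to 2% of the overall study population will have a gestational age <37 weeks". It then says openly that "There is no prespecified number of premature infants targeted for enrollment in the substudy".

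Section 9.9.1 repeats the share ("The sample size of Premature Infant Immunogenicity Substudy will be approximately 1% to 2% of the total enrolled participants") and the allocation ("The study will randomize premature infants in a 1:1 ratio to either V114 or Prevnar 13™ vaccination group"). It then sets up Table 5: "For demonstration, it is assumed that 25 participants in each vaccination group will be enrolled and 22 participants will be evaluable", the second figure being "based on the 90% evaluability rate". Table 5 gives within-group 95% intervals for IgG GMCs of 1, 5 and 10 at log-scale SDs of 1.0, 1.5 and 2.0, all with 22 infants per group. The sSAP carries the same text and figures in Section 3.9.1, Table 4.

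The summary in Section 9.1 refers the reader to the table in these terms: "Section 9.9.1 provides information about the expected variability of the IgG GMC given the sample size".

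**The concern.** Taken at face value, 1 to 2% of 2,400 split 1:1 is 12 to 24 infants per group, and the table assumes 25. The table varies the SD and the GMC but holds the number of infants at a single value, at the favourable end of a twofold range. With no enrolment target, nothing secures that number. Section 9.1 nevertheless points to the table for the variability to be expected at the substudy's sample size.

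If the share came out near 1%, the GMC intervals would be much wider than any reader of Table 5 would expect. The table is the only precision statement for the substudy, and Sections 2.1 and 4.2 say the premature-infant data will be pooled across the V114 program. A reader might therefore overrate what this study contributes.

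**Working it through.** **Inputs.** Total 2,400 and share 1 to 2% (Section 4.1); allocation 1:1, evaluability 90%, and SDs and GMCs (Section 9.9.1); intervals from a one-sample t-distribution on natural logs, exponentiated (Section 9.6.1).

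**Reproducing Table 5.** Evaluable: 25 × 0.90 = 22.5, taken as 22. Interval: GMC × exp(± t(0.975, n−1) × SD/√n). At n = 22 and SD 1.0, the half-width on the log scale is 2.080/√22 = 0.443, giving (0.64, 1.56) for GMC 1, as printed. The other eight cells also match to two decimals. A normal quantile would give (0.66, 1.52), so the stated t method was used. There is no calculation error.

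**Where 25 per group lies.** 2 × 25 = 50 infants; 50/2,400 = 2.08%. The upper end of the stated range is 2,400 × 0.02 = 48, or 24 per group. The gap is one infant per group. If the true share were 2%, a binomial count from 2,400 would reach 50 or more with probability about 0.40, so 50 is an ordinary outcome at that end. If the share were 1%, it would practically never happen (probability about 2 in a million).

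**Precision across the range.** Evaluable numbers are rounded down, as the plan rounds 22.5 to 22. The 1% case is also shown at 11, because 12 × 0.90 = 10.8 rounds to 11 by the usual rule.

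| Share | Per group | × 0.90 | n | Log half-width, SD 1.0 | Ratio to n = 22 | GMC 1, SD 1.0 | GMC 1, SD 2.0 |
|---|---|---|---|---|---|---|---|
| Table 5 | 25 | 22.5 | 22 | 0.443 | 1.00 | (0.64, 1.56) | (0.41, 2.43) |
| 2% | 24 | 21.6 | 21 | 0.455 | 1.03 | (0.63, 1.58) | (0.40, 2.49) |
| 1.5% | 18 | 16.2 | 16 | 0.533 | 1.20 | (0.59, 1.70) | (0.34, 2.90) |
| 1% | 12 | 10.8 | 11 | 0.672 | 1.52 | (0.51, 1.96) | (0.26, 3.83) |
| 1% | 12 | 10.8 | 10 | 0.715 | 1.61 | (0.49, 2.04) | (0.24, 4.18) |

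At 2%, Table 5 is right for practical purposes. If 21.6 is rounded to the nearest whole number, it is exactly right. The difference becomes material only in the middle and lower part of the range.

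**What depends on the table.** Sections 9.3 and 9.8 state that there is no hypothesis and no multiplicity adjustment. Section 9.9.1 calls the immunogenicity objectives descriptive. No power figure, enrolment target, stopping rule or decision criterion takes 22 or 25 as an input. The reported intervals will be computed from the infants actually available.

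**The case for a change.** The strongest case for a change is that the label of a demonstration does not fully excuse the table. Section 9.9.1 itself names sample size among the drivers of interval width, yet sample size is the one driver the table does not vary, and the sponsor controls it least. The SDs are described as representative of a previous study, so the wide intervals at low n are realistic. At SD 2.0 the ratio of upper to lower limit is 5.9 at n = 22 and 17.5 at n = 10. Nothing tells the reader that 22 is close to the best case. The response rate, also a secondary endpoint, has no precision statement: if every infant responded, the Clopper-Pearson lower limit, 0.025^(1/n), would be 69% at n = 10 against 85% at n = 22.

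Most of these facts stand. The table does illustrate only the upper end, and smaller substudies would be clearly less precise. Two limits apply. First, Table 5 covers IgG GMCs only, so it cannot overstate precision for response rates or OPA titers; the 69% and 85% figures would be new content and correct nothing already stated. Second, the 61% widening combines the 1% floor with rounding 10.8 down to 10; with 11 it is 52%.

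The inference that someone would be misled is weaker. The plan discloses the 1 to 2% range, the absence of a target and the n behind the table, and any reader can rescale the intervals. Pooling across the program will use actual counts.

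**Conclusion.** No change follows. No printed figure is wrong, and 25 per group agrees with the 2% end of an approximate range to within one infant per group (2.08% against 2%; intervals at most 2.7% wider on the log scale with 21 evaluable). What remains is that the single illustration sits at the favourable end. Intervals would be about 20% wider on the log scale at a 1.5% share and 52% to 61% wider at 1%, assuming 2,400 enrolled, an even split and 90% evaluability. That is missing detail in an illustration that the plan labels as such. Further rows would be harmless, but they would leave the endpoints, analysis sets, methods, conduct and conclusions as they are, because the substudy is descriptive and its reported intervals will reflect the observed numbers.
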